12.4 ADDITIONAL EFFICACY ANALYSES

The additional efficacy analyses will use the FAS population.

Additional efficacy analyses of continuous endpoints will use an MMRM model using baseline Hb and the parameter value as covariates and the other randomization stratification factors except baseline Hb (≤ 8 vs > 8), as fixed effects as outlined above. An ANCOVA model will be used for number of days hospitalized per PEY, rescue therapy used per PEY, etc. where MMRM model is not appropriate.

Additional analyses of proportions will use the CMH model adjusting for the randomization stratification factors. A CMH adjusted odds ratio and its associated 95% CI will be computed to compare between the roxadustat TIW group and pooled placebo. A two-sided 95% CI of the proportion based on the exact method of Clopper-Pearson will be computed for each treatment group.

Additional efficacy analyses of time-to-event endpoints will use the Cox Regression model. Median time to event and associated 95% CI will be estimated using Kaplan-Meier method.

Proportion of Hb values within 10.0-12.0 g/dL will be calculated in two ways:

Proportion of Hb values:

The following proportion in percentage for each subject will be defined:

*(Number of Hb values within 10.0-12.0 g/dL / Total number of protocol-planned Hb values) * 100* in weeks 28 to 36, 44 to 52 and 96 to 104 without use of rescue therapy within 6 weeks prior to and during this 8 week evaluation period. All scheduled and unscheduled hemoglobin

values that belong to each period will be taken into account using the analysis windows defined in Table 10.3-1.

Percentage of time:

[figure not shown]
The percentage of time each patient has Hb values within 10.0-12.0 g/dL will be calculated (as a percentage of the total of the length of time between the first and last Hb assessment during the evaluated period). The percentage of time will be calculated via linear interpolation. That is, if the change in Hb category (for instance from within 10.0-12.0 g/dL to > 12.0 g/dL) occurs between two visits V0 and V1, the day of change will be calculated by:

$$x = x_0 + (y - y_0) \frac{(x_1 - x_0)}{(y_1 - y_0)}$$

Where x_1 and x_0 are the dates when Hb was measured at V0 and V1 respectively, y_0 and y_1 are the Hb value at the respective visits V0 and V1 and y is the level of the Hb boundary (i.e. 12.0, 13.0 or 14.0g/dL).

Figure 11 shows visually how the linear interpolation will calculate the total number of days that a subject is in each Hb category for an example subject:

Figure 1: Example of Linear Extrapolation

In case that several Hb values are on the same day the average of these values will be used to represent the Hb of that day in the above formula. This calculation will provide the day that the change in Hb value occurs. The number of days that the Hb value has been in each category will

be determined and the percentage calculated based on the length of time between the first and last Hb assessment during the evaluated period, i.e.:

Date of Last Hb assessment during the evaluated period – Date of first assessment during the evaluated period.

No imputation will be performed if no Hb value is available in relevant time windows.

Rate of change in eGFR over time will be analyzed using the random effect model adjusted by baseline eGFR.

To evaluate Hb maintenance by other dosing frequencies, the following summary will be provided for the subgroups of subjects treated on BIW or QW (including any frequency <QW) for longer than 8 weeks (i.e., ≥ 56 days):

- Average Hb values over time for every 4-8 weeks after the initiation of BIW or QW
- Average weekly dose over time for every 4-8 weeks after the initiation of BIW or QW

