9.4.3.3 Additional Efficacy Analyses

The additional efficacy analyses will use the ITT population.

Additional efficacy analyses of continuous endpoints will use an MMRM model using baseline value as covariate and other stratification factors as fixed effects.

Additional analyses of proportions will use the CMH model adjusting for stratification factors. A CMH adjusted odds ratio and its associated 95% CI will be computed to compare between the roxadustat TIW group and pooled placebo. A two-sided 95% CI of the proportion based on the exact method of Clopper-Pearson will be computed for each treatment group.

Additional efficacy analyses of time-to-event endpoints will use the Cox Proportional Hazards model adjusting for stratification factors. Median time to event and associated 95% CI will be estimated using Kaplan-Meier method.

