3 STUDY DESIGN

This is a Phase 3, multi-center, randomized, double-blind, placebo-controlled study in anemic subjects with Stage 3, 4, or 5 CKD who are not on dialysis.

This study will consist of three study periods:

- **Screening Period:** Up to 6 weeks
- **Treatment Period:** Variable for individual subjects. In order to complete the Treatment Period simultaneously for all study subjects, the minimum treatment duration may be less than 52 weeks, with a maximum treatment duration of up to 3 years after the last subject is randomized.
- **Post-Treatment Follow-Up Period:** 4 weeks

3.1 IN ORIGINAL PROTOCOL AND AMENDMENT 1

Following the Screening Period, subjects are randomized to 1 of 6 treatment arms, defined by their dose frequency during maintenance (see Table 1). The randomization will result in a 2:2:2:1:1:1 ratio of subjects receiving roxadustat or placebo, respectively.

Randomization stratification factors include screening Hb values, cardiac/cerebrovascular/thromboembolic medical history, and estimated glomerular filtration rate (eGFR), and geographic region.

The Investigator, study site staff, subject, and the sponsor, are blinded to study drug, but not to dose or dosing frequency. Additionally, all efforts will be made to keep subjects blinded to study Hb values.

Study drug will be dosed TIW for anemia correction until subjects achieve a Hb value of ≥ 11 g/dL and ≥ 1 g/dL increase from baseline at two consecutive visits. Once these criteria are met, a dose frequency conversion to QW or BIW or a continuation of TIW will occur according to the subject's assigned treatment arm at randomization, defining entry into the maintenance phase.

Table 1. Study Drug Dose Frequencies

Treatment Arms	Correction	Maintenance	n (Roxadustat)	n (Placebo)
1A	TIW	QW	100*	0
1P	TIW	QW	0	50*
2A	TIW	BIW	100	0
2P	TIW	BIW	0	50
3A	TIW	TIW	100	0
3P	TIW	TIW	0	50

A=Active, P= Placebo

*These numbers are based on a sample size of 450 and would increase if overall sample size increases.

3.2 UNDER AMENDMENT 2 & 3

Following the Screening Period, subjects will be randomized in a 2:1 ratio to receive roxadustat (approximately 300-800 subjects) or placebo (approximately 150- 400 subjects). Randomization is stratified by the following factors:

- Screening Hb values (≤ 8 g/dL vs > 8 g/dL)
- History of cardiovascular, cerebrovascular or thromboembolic diseases (Yes vs No)
- eGFR (< 30 mL/min/1.73 m² vs ≥ 30 mL/min/1.73 m²)
- Geographic region (US vs Ex-US).

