 - Number of ESA-week dose per PEY: 1-3 doses of epoetin alfa or beta or biosimilar thereof (in Europe) administered within 1 week = 1 ESA-week; 1 darbepoetin subcutaneous (SQ) or IV dose = 2 ESA-week; 1 Mircera IV or SQ dose = 4 ESA-week
 - Time to (and proportion of subjects who receive) IV iron therapy in the first 24 weeks of treatment, and in treatment period
 - IV iron(mg) per patient-month (4 weeks) exposure to study medication
 - Exposure adjusted incidence rate of rescue therapy (composite, and individual component) per PEY, overall and sub-grouped by baseline Hb (≤ 8 g/dL, >8 g/dL)

Changes in cholesterol levels

- Change from baseline at each of the selected treatment time points (averaged over Weeks 12-28, and Week 36, 44 and 52) in:
 - Total cholesterol
 - Low-density lipoprotein/high-density lipoprotein ratio
 - Non-HDL cholesterol
- Proportion of subjects achieving LDL target of < 100 mg/dL for average LDL over Weeks 12 to 28

Blood pressure effect

- Proportion of subjects achieving blood pressure treatment goal in CKD subjects (systolic BP < 130 mmHg systolic and diastolic BP < 80 mmHg) based upon the average blood pressures over Weeks 12 to 28 of treatment

Health-Related Quality of Life (HRQoL) and European Quality of Life in Five Dimensions, Five Levels (EQ-5D-5L) benefits of anemia therapy in subjects with CKD anemia

- Mean CFB averaged over Weeks 12 to 28 of treatment in:
 - Vitality Subscale of SF-36
 - In subjects with baseline VT subscore below 50
 - Physical Functioning (PF) Subscale of SF-36
 - In subjects with baseline PF subscore below 50
 - Physical Component Scores of SF-36
 - In subjects with baseline physical component scores below 40
 - In all subjects

- Other component scores of SF-36
 - In all subjects
- Anemia Subscale (“Additional Concerns”) of Functional Assessment of Cancer Therapy-Anemia (FACT-An) Scores
 - In subjects with baseline subscale scores below 55 (generally associated with fatigue.)
 - In all subjects
- Total FACT-An Scores
 - In subjects with baseline FACT-An scores below 135
 - In all subjects
- EQ-5D-5L Scores
 - In all subjects

Hepcidin, CHr, Iron Parameters, HbA1c, and CKD Progression

- Change from baseline in serum hepcidin at each scheduled time point up to Week 52
- Change from baseline in CHr at each scheduled time point up to Week 52

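### The LDL-target and BP-goal proportions are compared by CMH without the subject's own baseline LDL or BP; the test is valid, but avoidable precision is lost

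*SAP*

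**What the plan says.** SAP 4.3 lists two responder-type endpoints among the additional evaluations: "Proportion of subjects achieving LDL target of < 100 mg/dL for average LDL over Weeks 12 to 28" and "Proportion of subjects achieving blood pressure treatment goal in CKD subjects (systolic BP < 130 mmHg systolic and diastolic BP < 80 mmHg", the latter also based on the average over Weeks 12 to 28. Neither is restricted to, or split by, subjects who were off target at entry.

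SAP 12.4 gives the method: "Additional analyses of proportions will use the CMH model adjusting for the randomization stratification factors". Protocol 9.4.3.3 has the same rule: "Additional analyses of proportions will use the CMH model adjusting for stratification factors". SAP section 3 lists four two-level factors: "Screening Hb values (≤ 8 g/dL vs > 8 g/dL"), "History of cardiovascular, cerebrovascular or thromboembolic diseases (Yes vs No"), eGFR below 30 versus 30 or more, and US versus Ex-US. That makes 16 cells, none defined by LDL or BP.

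Elsewhere the SAP does use the endpoint's own baseline:
- For additional continuous endpoints, SAP 12.4 says: "Additional efficacy analyses of continuous endpoints will use an MMRM model using baseline Hb and the parameter value as covariates". In context this means the parameter's baseline value.
- SAP 12.3 item 5 includes baseline LDL in the secondary LDL model. Item 11 (MAP) refers back to the same type of model, and the protocol synopsis confirms baseline value as covariate for both.
- SAP 4.3 adjusts doubling of serum creatinine for baseline creatinine.
- SAP 12.2.4 repeats the Hb responder analysis by logistic regression with continuous baseline Hb and eGFR.

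**The concern.** Whether a subject's average LDL or BP over Weeks 12 to 28 falls below a fixed threshold will usually depend on where that subject started. Protocol 5.2 sets no LDL limit and excludes only systolic BP of 160 mmHg or more or diastolic BP of 95 mmHg or more, so subjects can enter already at target. A comparison that leaves out the starting value treats all of that baseline variation as unexplained.

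At stake is the width of the confidence intervals for these two endpoints. The SAP gives no reason for handling the binary versions differently from the continuous ones.

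**Working it through.** **1. The plan's own figure.** No power or sample size is stated for either endpoint. The only binary power statement (SAP 5.1) is for the Ex-US primary: 65% versus 25%, 450 subjects, two-sided 5%, power above 95%. With 300:150, the pooled rate is (300 × 0.65 + 150 × 0.25)/450 = 0.517. The pooled SE is √(0.517 × 0.483 × (1/300 + 1/150)) = 0.0500. The unpooled SE is √(0.65 × 0.35/300 + 0.25 × 0.75/150) = 0.0448. Then z = (0.40 − 1.96 × 0.0500)/0.0448 = 6.74, so power exceeds 99.9%. The statement reproduces but does not concern LDL or BP.

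**2. Inputs.**
- From the documents: the 16 strata, two-sided 5%, 2:1 allocation, and 300:150 (minimum) to 800:400 (maximum).
- Assumed: correlation ρ between baseline and on-study value of 0, 0.3, 0.5 or 0.7; treatment shift of 0.2 or 0.3 SD; 30% or 50% at target at baseline; stratum prevalences of 10% (Hb), 35% (CV history), 70% (eGFR below 30) and 30% (US), unrelated to outcome.

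**3. Model.** Baseline z is standard normal and follow-up is ρz + √(1 − ρ²)e − shift × treatment. A subject is at target if follow-up is below the threshold c that gives the assumed baseline share. There were 2,000 trials per scenario (simulation error about 1 point).

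Hand check of the unadjusted power at 300:150, shift 0.3 SD, 50% at target: the rates are Φ(0.3) = 0.618 and 0.500, a difference of 0.118. The pooled SE is 0.0494 and the unpooled SE 0.0495, so z = (0.118 − 1.96 × 0.0494)/0.0495 ≈ 0.43 and power is about 66%. The simulated CMH gives 63.5% to 65.6%, whatever the correlation.

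**4. Power, planned CMH → logistic with continuous baseline (%).**

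| Allocation, shift, share at target at baseline | ρ = 0.3 | ρ = 0.5 | ρ = 0.7 |
|---|---|---|---|
| 300:150, 0.2 SD, 30% | 33.9 → 36.6 | 31.5 → 36.4 | 30.2 → 43.1 |
| 300:150, 0.2 SD, 50% | 34.6 → 36.2 | 32.9 → 39.7 | 34.5 → 47.6 |
| 300:150, 0.3 SD, 30% | 63.5 → 66.7 | 61.2 → 70.6 | 62.7 → 79.8 |
| 300:150, 0.3 SD, 50% | 63.8 → 66.4 | 63.5 → 73.2 | 65.4 → 82.7 |
| 800:400, 0.2 SD, 30% | 70.5 → 72.6 | 70.7 → 78.9 | 70.7 → 86.4 |
| 800:400, 0.2 SD, 50% | 72.1 → 75.0 | 73.2 → 80.5 | 73.2 → 88.8 |
| 800:400, 0.3 SD, 30% | 96.4 → 97.5 | 96.3 → 98.6 | 96.5 → 99.6 |
| 800:400, 0.3 SD, 50% | 97.7 → 98.7 | 97.8 → 98.9 | 96.9 → 99.7 |

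Subtracting within the first six rows, the gain is 1.6 to 3.2 points at ρ = 0.3, 4.9 to 9.7 at 0.5 and 12.9 to 17.3 at 0.7. In the last two rows, where CMH power is already at least 96%, it is 1.0 to 3.1 points. At ρ = 0 the gain is at most 1.3 points, within simulation error.

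**5. An at-target stratum instead of continuous baseline.** Adding at target yes/no at baseline to the CMH strata changes power, in the same six scenarios, by −1.1 to 1.8 points at ρ = 0.3, 1.1 to 4.4 at 0.5 and 7.0 to 10.1 at 0.7. It recovers only part of the gain.

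**6. Validity.** With no treatment effect the planned CMH rejects in 4.4% to 5.8% of trials, which is nominal within simulation error.

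**7. Chance imbalance.** At 300:150 with 50% at target at baseline, the between-group difference in that share has SD √(0.25 × (1/300 + 1/150)) = 5 points. With 50% at target, the at-target rate at follow-up differs by (2/π)·arcsin ρ between subjects at and not at target at baseline. A one-SD imbalance therefore moves the unadjusted risk difference by about 1.0, 1.7 and 2.5 points at ρ = 0.3, 0.5 and 0.7, against a true difference of 11.8 points for a 0.3 SD shift.

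**The case against.** The strongest reply is that nothing depends on these tests. Both endpoints sit outside the fixed sequence, carry no multiplicity adjustment (SAP 5.3) and have no power target. The multiplicity-controlled LDL and MAP analyses already use baseline. All of that stands, and it limits the point to an improvement.

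A reader might go further than the documents allow in four ways.
- *That the planned comparison is biased by chance imbalance at baseline.* It is not. Under randomisation such imbalance is covered by the error rate and the confidence interval. It is imprecision.
- *That subjects already at target merely add noise.* They can lose the target and so carry information on the effect. The loss comes from unexplained baseline variation in all subjects, which is why step 5 recovers only part of it.
- *That a large power loss is established.* The correlation, the effect and the share at target are not in the documents, and the gain runs from almost nothing to about 17 points. The model uses a single threshold. The BP goal has two components and its baseline is truncated by eligibility, so no figure is claimed for BP. SAP 12.4 also names roxadustat TIW versus pooled placebo for the CMH odds ratio, and the size of that comparison is not fixed.
- *That CMH should be replaced at no cost.* CMH matches the protocol and needs no linear-logit assumption. The SAP's own pattern in 12.2.4 is to run logistic regression alongside it. A logistic odds ratio conditional on baseline is a different quantity from the CMH odds ratio, so the two should not be compared as if one were simply more precise.

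**Conclusion.** The point holds as a minor efficiency and consistency issue. The plan leaves out a baseline value that is collected, that SAP 5.4 defines (specifically for BP, by the general rule for LDL), and that the SAP uses for the continuous versions of the same measures. The planned CMH is valid and no confirmatory conclusion changes.

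On the assumed inputs, continuous baseline adjustment is worth no more than about 3 points of power at a correlation of 0.3, about 5 to 10 at 0.5 and about 13 to 17 at 0.7, and little where power is already near 100% (800:400 with a 0.3 SD shift). These figures rest on a normal single-threshold model with strata unrelated to outcome. They illustrate the LDL endpoint and indicate only the direction for BP.

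**What to change.** In SAP 12.4, keep the CMH and add for these two endpoints a logistic regression on treatment, continuous baseline LDL (for BP, baseline systolic and diastolic BP), baseline Hb, baseline eGFR, CV history and region, following SAP 12.2.4. Report a standardised risk difference with 95% CI as the main adjusted estimate. SAP 12.2.4 does not produce one, but the SAP reference list already includes a methods paper on covariate-adjusted differences in proportions from logistic regression. Tabulate results by at-target status at baseline.

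State which comparison the model serves: SAP 12.4 names TIW versus pooled placebo for these proportions, whereas SAP 5.3 says most tables compare pooled roxadustat with pooled placebo.

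The cost is small: one extra model per endpoint using data already collected, a linear-logit assumption, a conditional odds ratio that must be labelled as distinct from the CMH odds ratio, and a note of the change from protocol 9.4.3.3 in the SAP and study report, in line with protocol 9.5.

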6. Time to (and proportion of subjects with) protocol defined worsened hypertension for the pooled roxadustat vs pooled placebo will be compared using Cox Proportional Hazards model adjusting for stratification factors. A hazard ratio and its associated 95% CI will be computed between the roxadustat group versus pooled placebo. Noninferiority will be declared if the upper bound of the 2-sided 95% CIs of the odds ratio does not exceed 1.3. Superiority will be declared if the upper bound of the 2-sided 95% CI of the odds ratio does not exceed one. The incidence rate per PEY by treatment group will also be reported.
7. Time to (and proportion of subjects who received) rescue therapy (composite of RBC transfusion, ESA use, and IV iron) over the first 24 and first 52 weeks for the roxadustat TIW group versus pooled placebo will be compared using Cox Proportional Hazards model adjusting for stratification factors. A hazard ratio and its associated 95% CI will be computed between the roxadustat group versus pooled placebo. Superiority will be

declared if the upper bound of the 2-sided 95% CI of the hazard ratio does not exceed one.

Comparisons of the individual treatment arms from the original and Amendment 1 versions of the protocol (ie, BIW, QW) in roxadustat against pooled placebo will be reported descriptively. Subgroup analyses will also be performed for primary and secondary endpoints by sex, age group, etc.

Due to the large amount of visits to include in the model, the unstructured covariance pattern model will be applied first. If the algorithm for unstructured covariance pattern does not converge, then the heterogeneous Toeplitz structure will be used instead. If this second model also does not converge, then the (homogeneous) Toeplitz structure will be tried, and finally compound symmetry as a covariance structure to achieve convergence.

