5.2.3 Full Analysis Set (FAS)

The FAS consists of all randomized/enrolled subjects who received at least one dose of study drug and have baseline and at least one post-dose Hb assessment. If actual treatment received differs from the randomized treatment arm, the randomized treatment arm will be used for analysis for the FAS except for analyses by maintenance dosing frequency which will be presented as-treated. This analysis set is primarily used for EX-US submissions.

FAS1 is a subset of FAS subjects who are randomized/enrolled prior to Amendment 2. FAS2 is a subset of FAS subjects who are randomized/enrolled under Amendment 2 or later.

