5.3 METHODOLOGY AND CONVENTIONS

Continuous variables will be presented by descriptive statistics: n, mean, standard deviation, median, minimum, and maximum. Categorical variables will be presented by frequency count and percentage.

Lab results obtained from the central laboratory, rather than local laboratories, will be used for all efficacy and safety analyses. Local laboratory values, if collected in the CRF's, will be listed.

The treatment groups will be presented as follows:

Roxadustat QW(1A), Roxadustat BIW(2A), Roxadustat TIW(3A), Pooled Roxadustat (1A+2A+3A), Pooled Placebo (1P+2P+3P). Most safety and efficacy tables will be presented by Pooled Roxadustat vs. Pooled Placebo. Selected safety and efficacy tables will present randomized treatment arms of QW, BIW and TIW if the patient received the actual maintenance dosing frequency for QW, BIW and TIW. In these tables, Roxadustat subjects who were randomized to BIW or QW under Amendment 1 but never switched (e.g., due to Amendment 2) to that maintenance frequency will not be presented in BIW or QW group, but in the TIW and pooled Roxadustat groups.

The statistical comparisons will be done between roxadustat against Placebo as deemed appropriate, where the groups before amendment 2 are pooled

Unless otherwise stated, all statistical tests will be two-sided hypothesis tests performed at the 5% level of significance for main effects and all confidence intervals will be two-sided 95% confidence intervals.

The primary and secondary endpoints will be tested sequentially using the fixed sequence approach for multiplicity adjustments at an alpha level of 0.05. There will be no adjustments for multiple comparisons for other tests.

All analyses will be performed using SAS[®] Version 9.1.3 or higher.

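### SAP 12.4 compares additional proportion endpoints only between an undefined roxadustat TIW group and pooled placebo; under the SAP's own frequency rules that group depends on post-randomisation Hb response

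*SAP*

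**What the plan says.** SAP 12.4 sets the method for additional proportions, a CMH analysis adjusted for the randomisation stratification factors, and gives one contrast: "A CMH adjusted odds ratio and its associated 95% CI will be computed to compare between the roxadustat TIW group and pooled placebo". The analysis set is stated there too: "The additional efficacy analyses will use the FAS population". The wording follows protocol 9.4.3.3, which also plans "to compare between the roxadustat TIW group and pooled placebo".

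Three other places bear on who is in that group.

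- SAP 5.2.3 analyses the FAS by randomised arm, "except for analyses by maintenance dosing frequency which will be presented as-treated".
- SAP 5.3 labels the TIW arm as 3A. It adds that, in selected tables, subjects randomised to BIW or QW under Amendment 1 who never changed frequency "will not be presented in BIW or QW group, but in the TIW and pooled Roxadustat groups".
- SAP 3.1 ties the change of frequency to Hb (at least 11 g/dL with a rise of at least 1 g/dL, at two consecutive visits): "Once these criteria are met, a dose frequency conversion to QW or BIW or a continuation of TIW will occur".

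SAP 5.3 also says that most tables will compare pooled roxadustat with pooled placebo, and SAP 12.3 makes that the default for the secondary endpoints.

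**The concern.** Before Amendment 2, subjects in arms 1A and 2A left TIW dosing only after an Hb response. If the as-treated rules define the TIW group, responders who switched are removed from it and non-responders stay. The placebo arms are pooled whatever their assigned frequency, so nothing comparable is removed from the comparator. The odds ratio would then compare a group partly selected on a treatment outcome with an unselected one, and randomisation no longer protects it. Treated subjects are also discarded without a stated reason. At stake is the only odds ratio planned for these endpoints, such as the proportions reaching the LDL target, reaching the BP goal, or having a 30%, 40% or 50% fall in eGFR.

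**Working it through.** The SAP gives no power or effect figure for the additional proportions. Its one power statement for a proportion (SAP 5.1: 65% against 25%, 450 subjects, two-sided 0.05, above 95%) reproduces: 300 against 150 gives more than 99.99%. That figure is not in dispute; its rates serve as inputs here.

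**Inputs**
- Response 65% on roxadustat and 25% on placebo (SAP 5.1). Using 65% as the chance of meeting the switching criterion is an approximation, because the ex-US response definition differs for baseline Hb of 8 g/dL or less and excludes rescued subjects.
- Three equal roxadustat arms of 100 before Amendment 2 (SAP Table 1), so 2/3 of those subjects were assigned to switch.
- f, the share of roxadustat subjects enrolled before Amendment 2, and s, the share of 1A/2A responders who actually switched. The documents give neither, so both are varied.

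**Composition of the TIW group (as-treated reading).** Only responders leave, so

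non-responder share = 0.35 / (1 − f × 2/3 × 0.65 × s).

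For f = 1 and s = 1: 0.35 / (1 − 0.433) = 0.35 / 0.567 = 62%.

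| f | s = 1 | s = 0.5 | s = 0 |
|---|---|---|---|
| 0.25 | 39% | 37% | 35% |
| 0.50 | 45% | 39% | 35% |
| 1.00 | 62% | 45% | 35% |

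**Effect on an outcome fully tied to response.** Hb response itself is used as the extreme case.
- As randomised: (0.65/0.35) / (0.25/0.75) = 5.57.
- N = 450, all enrolled before Amendment 2, s = 1: arm 3A contributes 65 responders and 35 non-responders. Arms 1A/2A lose their 130 responders and contribute 70 non-responders. The group has 170 subjects, 65/170 = 38.2% responders, and an odds ratio of (65/105) / (0.25/0.75) = 1.86.
- N = 1200, assuming 300 roxadustat subjects before and 500 after Amendment 2, s = 1: 65 + 325 = 390 responders and 105 + 175 = 280 non-responders. The group has 670 subjects, 58.2% responders, and an odds ratio of 4.18.
- With s = 0.5 the two odds ratios are 3.71 and 4.88. With s = 0 both are 5.57.

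The rule multiplies the odds ratio by 1 − f × 2/3 × s. With no true effect and s = 1 it therefore produces 1 − 2/3 = 0.33 at N = 450, and 1 − 0.375 × 2/3 = 0.75 at N = 1200 (f = 300/800 = 0.375).

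**Alternative reading (arm 3A as randomised).** Nothing is selected on response, but 200 of 300 pre-Amendment 2 roxadustat subjects (two thirds) are left out while all placebo subjects stay. The pre-Amendment 2 comparison becomes 100 against 150, against 2:1 afterwards. The CMH strata do not include enrolment period.

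**The case against.** The strongest reply is that SAP 12.4 never says that its TIW group is the as-treated one. SAP 5.3 labels TIW as 3A, its reassignment rule covers selected tables, and SAP 5.2.3 applies as-treated grouping only to analyses by maintenance frequency. This stands: selection on response follows from one reading, not from an explicit definition. It does not rescue the sentence, because the other reading discards subjects and the text does not say which applies.

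Several stronger conclusions that a reader might draw are not supported.

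- *The TIW group loses every BIW/QW responder.* SAP 3.2 keeps pre-Amendment 2 subjects who had not yet changed frequency on TIW, so some responders stay. The group also holds arm 3A and everyone enrolled from Amendment 2 on. The 62% figure needs full switching and no later enrolment, yet the SAP defines subsets for later enrollees and plans analyses in them.
- *All the additional endpoints are biased against roxadustat.* The documents do not relate Hb response to LDL target, BP goal or eGFR decrease. The Hb-responder primary and the secondary proportion with Hb of at least 10 g/dL (SAP 12.3 item 3) are pooled comparisons and are not governed by this sentence.
- *Every other main comparison is pooled.* SAP 12.3 item 4 tests the frequencies separately within the fixed sequence, in roxadustat responders only, and protocol 9.4.3.1 does so for the US primary endpoint.
- *The rescue-therapy analysis has the same fault.* Protocol 9.4.3.2 item 7 does say "for the roxadustat TIW group versus pooled placebo will be compared using Cox Proportional Hazards model", but SAP 12.3 item 6 now names the roxadustat group for the 52-week endpoint. The Cox sentence in 12.4, which covers the 24-week endpoint, names no TIW group.

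It is also fair that TIW is the current regimen, so a TIW result has descriptive interest.

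**Conclusion.** The concern holds in limited form. The only odds-ratio contrast for the additional proportions uses an undefined group. On the as-treated reading it is not a randomised comparison; on the 3A reading it omits two thirds of pre-Amendment 2 roxadustat subjects. Both depart from the SAP's pooled-against-pooled convention. The size rests on the planned 65% response, equal arms and two unknown shares: a non-responder share of 37% to 62% across the settings with switching, against 35% as randomised, and no distortion if nobody switched. Bias against roxadustat can be stated only for outcomes tied to Hb response. The endpoints lie outside the fixed sequence and carry no multiplicity adjustment, so no primary or secondary conclusion is affected.

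**What to change.** In SAP 12.4, replace *roxadustat TIW group* with *pooled roxadustat*, grouped as randomised, against pooled placebo. Add that this supersedes the wording of protocol 9.4.3.3; with that note, no protocol edit is needed for this point. Any TIW-only result should be descriptive, with a statement of whether the group is arm 3A as randomised or the as-treated group, and how subjects enrolled from Amendment 2 on are counted. The rescue-therapy analyses need no separate change. The cost is one phrase and one sentence in the SAP, with no new data or analysis method.
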